A total of 36 individuals will be recruited for this study, 18 in each group. Approximately 60% in each group will be female. The primary outcome measure of this study is the change in absolute FPA performance error (the difference between the performed and the targeted FPA), which is indicative of how ‘accurate’ the patient is when performing the modification. This outcome measure is only relevant to the SMOD group, who have a specific target for their modification; therefore, allowing an error value to be calculated. This outcome will be measured during immediate and delayed retention at week one compared to follow-up and will provide evidence of the extent to which motor learning has occurred. Previous FPA performance error during immediate retention testing after a six-week FPA modification resulted in a small effect (Cohens $d = 0.35$) [3]. We are also interested in exploring the clinical and biomechanical differences between the SMOD and AMAC gait modification groups; however, no study has previously compared these methods of gait modification. Therefore, we will be conservative and base our sample size calculation on the between-within interaction effect of a 2×4 (group = 2: SMOD vs AMAC; measure = 4: immediate and delayed retention tests at week 1 and follow up) repeated measures ANOVA with an effect size of $f = 0.175$ ($f = d / 2$). With power = 0.8 and alpha = 0.05, a total sample of 30 is required [4]. With a conservatively estimated attrition of 15%, we will recruit 36 participants total (18 per group).

Procedures

Recruitment and screening

Volunteers will be recruited via print and social media, and via our database of previous participants who have indicated interest in participating in future studies. Interested volunteers will be screened via phone, email, or our lab website by the study coordinator to assess inclusion and exclusion criteria. Those deemed preliminarily eligible will be invited to attend a gait screening appointment. Eligible participants who pass the gait screen will be referred for a radiographic assessment of their knees to confirm the presence of structural signs of knee OA.

Standing, semi-flexed posteroanterior radiographs of both knees will be taken. A trained assessor will grade all radiographs based on the KL criteria. Those passing all screening requirements will be invited to enroll in the study.

Gait screening

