Official Title: Foot progression angle modification: an exploratory six-week intervention in people with knee osteoarthritis.

NCT Number: TBD

Document Date: Mar 24th, 2020

Statistical Analysis Plan

Statistical analyses will be performed by an independent statistician. Means and standard deviations will be calculated for each outcome measure and baseline demographic characteristic. Baseline demographic data (e.g. age, body mass index, disease severity) will be examined for between-group differences using unpaired two-tailed t-tests. For all statistical analyses, alpha will be set to 0.05. Any multiple pairwise comparisons will be adjusted using the Bonferroni correction method.

Data will be assessed for sphericity, homoscedasticity, and normality using Mauchley's test, residual versus predicted plots, and quantile-quantile plots. Homoscedasticity and normality assumptions will be confirmed using Levene's test and Shapiro-Wilk's test, respectively. Sphericity assumption violations will be corrected for using the Greenhouse Geisser approach. Violations of homoscedasticity will be corrected for by bootstrapped model parameters. If normality is not met, a non-parametric test will be used.

Primary Hypotheses:

Repeated measures analyses of variance (ANOVA) will be performed to examine the within-group changes in learning outcomes over the six-week intervention. Between-group differences will be examined using a two-way mixed ANOVA, with the repeated measure being the learning outcome (foot progression angle change from baseline during in-lab and at-home walking) and the between-subject factor being group assignment (SMOD vs AMAC).

Secondary Hypotheses:

Biomechanical (knee joint moments), clinical (NRS knee pain, KOOS pain, symptoms, and physical function scores), and difficulty (difficulty of performing the FPA modification) change scores will be examined using an analysis of covariance (ANCOVA) with significant between-group baseline demographic group differences and baseline outcome values included as covariates.

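### The retention tests are modelled as one four-level factor that mixes time with test type, and no week-1-to-follow-up contrast is named as the test of learning

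*Protocol*

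**What the plan says.** The Protocol, under Participants, states: "The primary outcome measure of this study is the change in absolute FPA performance error". It adds: "This outcome measure is only relevant to the SMOD group, who have a specific target for their modification". The comparison is put in terms of time: "This outcome will be measured during immediate and delayed retention at week one compared to follow-up", as evidence of motor learning.

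The same paragraph then chooses to "base our sample size calculation on the between-within interaction effect of a 2×4" repeated measures ANOVA, in which the repeated factor is "measure = 4: immediate and delayed retention tests at week 1 and follow up". With f = 0.175, alpha 0.05 and power 0.8, this gives 30 participants in total, raised to 36 for 15% attrition.

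Under Gait modification intervention, retention tests are placed before practice (from the second session) and after practice. I take these to be the delayed and the immediate test respectively. The four levels therefore differ in more than time.

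The SAP does not repeat the 2×4 layout. Under Primary Hypotheses it plans repeated measures ANOVAs for within-group change over the six weeks. It also plans a two-way mixed ANOVA whose repeated measure is the learning outcome, described as "foot progression angle change from baseline during in-lab and at-home walking". Bonferroni adjustment applies to any multiple pairwise comparisons. Neither document lists the levels of the SAP's repeated factors, names a time contrast, or says which test or pair would count as learning.

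**The concern.** Two times crossed with two test types make a 2×2 within-subject layout. Treated as one factor with four levels, its test has 3 degrees of freedom and asks only whether any of the four means differ. The primary question has 1 degree of freedom: is error lower at follow-up than at week 1?

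Two things follow. First, a significant four-level main effect in SMOD could come from change over time, from a difference between immediate and delayed tests, or from both. The pairwise step resolves this only if the pairs are chosen suitably, and the plan does not choose them. Second, spreading a 1-df effect over 3 df, and then over Bonferroni-adjusted pairs, costs power in an arm of only 15 to 18 people. This matters most for the primary outcome, because it exists only in SMOD and so has to be tested within that arm.

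**Working it through.** **Inputs from the Protocol (Participants).** d = 0.35, reported for immediate retention testing only; f = d/2 = 0.175; m = 4 measures; two groups; alpha 0.05; N = 30 (15 per arm), 36 recruited (18 per arm).

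**Assumptions, because the documents give none.** Correlation ρ among the repeated measures, taken as 0.5 to 0.8; compound symmetry with no sphericity correction (epsilon 1); the size of any immediate-to-delayed loss; Bonferroni over all six pairs of the four means.

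**1. The plan's own figure.** For the interaction, λ = f²·N·m/(1−ρ), with df 3 and (30−2)×3 = 84. At ρ = 0.68, λ = 0.030625 × 30 × 4 / 0.32 = 11.48 and power is 80.2%. N = 30 is the required total for ρ from 0.68 to 0.70. At ρ = 0.5 the total would be 46 (power at 30: 59.1%); at ρ = 0.8 it would be 20. Attrition: 30/0.85 = 35.3, so 36. I use ρ = 0.68 as the reference case.

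**2. Interaction, same λ, effect wholly on time.** Group by measure has df (3, 84); group by time has df (1, 28). Power at N = 30:

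| ρ | 3 df | 1 df |
|---|---|---|
| 0.5 | 59% | 74% |
| 0.68 | 80% | 90% |
| 0.7 | 83% | 92% |

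**3. SMOD alone, true change of δ = 0.35 SD on both test types.** λ = n·4·(δ/2)²/(1−ρ). With n = 15 and ρ = 0.68, λ = 15 × 4 × 0.030625 / 0.32 = 5.74. The omnibus has df (3, 42) and the time contrast df (1, 14).

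| n | ρ | Omnibus, 3 df | Time contrast, 1 df |
|---|---|---|---|
| 15 | 0.5 | 30% | 43% |
| 15 | 0.68 | 46% | 61% |
| 15 | 0.7 | 49% | 63% |
| 18 | 0.68 | 55% | 70% |

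If learning requires a significant omnibus and then a Bonferroni-significant like-for-like pair (immediate with immediate, or delayed with delayed, across time), simulation at n = 15 and ρ = 0.68 gives about 22%.

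**4. SMOD alone, no change over time, immediate-to-delayed loss of g.** A test-type difference enters the omnibus λ exactly as a time difference of the same size does, so the omnibus cannot tell them apart. With g = 0.35 SD and n = 15 it rejects in 30%, 46% and 49% of trials at ρ = 0.5, 0.68 and 0.7. The time contrast stays at 5%. With g = 0.5 SD and ρ = 0.68:
- omnibus alone: 79%;
- omnibus plus an adjusted like-for-like pair: 1.7%;
- omnibus plus the mixed pair of week-1 delayed against follow-up immediate: 30%.

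**5. Change on the delayed test only (0.35 SD, n = 15, ρ = 0.68).** The omnibus has λ = n·(3/4)·δ²/(1−ρ) = 15 × 0.75 × 0.1225 / 0.32 = 4.31, power 35%. The averaged time contrast sees half the change, so λ = 5.74/4 = 1.44, power 20%. The omnibus plus a like-for-like Bonferroni pair gives about 12%.

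**The case against.** The strongest reply is that neither document commits to a four-level omnibus as the primary test. The 2×4 appears only in the sample-size text. The SAP speaks of within-group change over six weeks, H1 is worded from week 1 to week 6, and the primary outcome is worded as week 1 against follow-up. This stands, and it limits the point to a gap in specification. It does not close the gap: the 2×4 is the only model given for the retention tests, and the SAP puts no contrast in its place.

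Three stronger readings are tempting, and the documents do not support them.

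- *The plan would declare forgetting to be learning in 30–49% of trials.* That rate needs a bare SMOD omnibus, or a mixed pair, to be read as learning, and nobody in the plan says it will be. It also needs an assumed loss of 0.35 SD. The documents do not say that delayed tests will be worse, and their d = 0.35 is not an immediate-to-delayed difference. Like-for-like Bonferroni pairs keep the false rate below 2%.
- *Forgetting would make the powered test significant.* Forgetting common to both arms cancels in the group-by-measure interaction; only a difference in forgetting between arms would show there.
- *The SAP merges walking context with week.* Its in-lab and at-home phrase describes the outcome. Factor levels are unstated, and separate models fit the wording equally well.

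The power gain is also not universal. If change falls on one test type only, the averaged time contrast does worse than the omnibus (20% against 35%). But a significant omnibus does not by itself show change over time, and the omnibus-plus-pair route that would show it reaches about 12%.

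**Conclusion.** The point holds as a specification gap with a real cost in power. The question is one of time, the only model given for the retention tests mixes time with test type, and no contrast is named.

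At ρ = 0.68, with equal change on both test types, the 1-df time contrast gains about 15 points over the SMOD omnibus, about 39 points (61% against 22%) over the omnibus followed by like-for-like Bonferroni pairs, and about 10 points for the between-arm interaction. These sizes rest on compound symmetry, the assumed ρ and the Protocol's d = 0.35 applied to both test types. The ordering in favour of the time contrast held at each ρ tested when the effect lies equally on both tests.

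A reader might infer that a significant primary result would be uninterpretable. That goes too far: it would be so only if the omnibus or a mixed pair were taken as the evidence of learning, which the plan leaves open but does not require.

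**What to change.** In the SAP:

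- Analyse the retention tests with two within-subject factors: time (week 1, follow-up) and test type (immediate, delayed).
- Make the 1-df time effect in SMOD, averaged over test type, the primary test on absolute error.
- Make group by time the between-arm test, for outcomes that exist in both arms. Absolute error does not exist in the self-directed arm.
- Report test type and time by test type, so that a change confined to one test is seen.
- State that in-lab and at-home walking are modelled separately, or with context as its own factor.
- State the correlation assumed in the sample-size calculation.

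The cost is wording only: same data, same software, and no larger N for the interaction at ρ = 0.68. Two limits remain. The averaged contrast is weaker than the omnibus if only one test type changes. The SMOD time contrast also stays below 80% power with 15 to 18 people unless ρ is about 0.8 (80% at n = 15, 88% at n = 18), and the report should say so.

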Stair ascent and descent will be performed while wearing the sensorized shoes. This will take place at a building nearby the laboratory (5-minute walk) because of the availability of continuous linear sets of stairs for multiple flights. This allows the use of the sensorized shoe for measuring FPA during stair ascent and descent. These FPA data will be compared with transfer test data (details included below) examined at several points throughout the intervention. These same shoes will be provided to the participant to measure real-world FPA during at-home and community walking.

Sensorized shoes

A custom inertial sensor consisting of a 3-axis accelerometer (signal range: $\pm 4g$), gyroscope ($\pm 500^\circ/s$), and magnetometer ($\pm 1200\mu T$), sampling data at 100 Hz will be embedded in the sole of the shoe. A previously published custom sensor fusion algorithm [13], programmed into a microcontroller, calculates the FPA in real time and stores it on a microSD card for later extraction. The sensorized shoe design and algorithm has been validated during treadmill [14] and over-ground walking [15] with excellent validity and reliability (absolute error = 1.7° and intraclass correlation coefficients > 0.9).

Randomization

Once deemed eligible and baseline data collection is complete, each participant will be randomized to either the SMOD or AMAC group. Randomization will be performed using an *a priori* block-stratified approach based on sex and KL grade. A predetermined randomization matrix will be computed [16] by a team member not involved in testing or the intervention. Group allocations will be stored in opaque envelopes, which will be opened in a sequential manner after baseline testing and before the first practice session. The group allocation will be communicated to the study trainer via email.

Gait modification intervention

Both groups will attend six practice sessions conducted weekly, which will last approximately 1 hour each. Walking practice will be conducted on a treadmill with a full-length mirror placed

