directly in front of the treadmill. The SMOD group will be guided to increase their FPA by 15° in either the toe-in or toe-out direction (determined by the gait screen). A line of tape will be aligned on the mirror according to the target FPA, as we have done previously [5, 17]. This mirror-based method of providing a target for the FPA modification was shown to be similarly effective when compared to feedback delivered using an expensive real-time motion capture system, but with significantly greater clinical feasibility. The AMAC group will be instructed to increase their FPA by “as much as is comfortable”. The mirror will be provided during practice sessions; however, no tapeline will be placed. The amount of time spent with the feedback (mirror) visible will be progressively reduced (faded feedback) across the six weekly practice sessions in order to reduce the reliance on feedback [18]. Before and immediately after the practice sessions, the participant will perform a warm-up and cool-down walk while wearing the sensorized shoes (10-minute outdoor standardized walking loop). This will provide a repeatable non-laboratory-based measure of FPA. Both groups will be encouraged to practice their gait modification at any opportunity during their daily at-home walking. Practice sessions will be led by a kinesiologist with experience delivering gait modification interventions.

Learning will be measured during 1) practice, 2) immediate and delayed retention tests, 3) dual-task tests, 4) transfer tests, and 5) during at-home/community walking. Each test (2-4) will last 1 min and be collected at each practice session. For the SMOD group, the absolute performance error (absolute error = |performed FPA – target FPA|), FPA variability, and the proportion of steps with >7° of change from baseline FPA will be measured using the sensorized shoe. For the AMAC group, FPA variability and the proportion of steps with >7° of change from baseline FPA will be measured. Retention tests will occur immediately before (starting at practice session 2) and after practice bouts. The participant will be asked to perform their gait modification as accurately as possible for 1 minute. Dual-task testing will be performed identically to the baseline assessment described above; however, the participant will be asked to simultaneously perform their gait modification. Lastly, transfer testing will be performed during stair ascent and descent in the same manner as the baseline assessment.

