During each practice session, participants will be asked to rate their knee pain at the beginning, middle, and end of the session using an 11-point numerical rating scale (0 = “no pain” and 10 = “worst pain imaginable”). At the end of the sessions, they will be asked to rate the difficulty in achieving their FPA modification during that practice period using an 11-point numerical rating scale (0 = “not difficult” and 10 = “most difficult/unable to perform”).

An instructional booklet will be provided which outlines details of how to care for and use the sensorized shoes while at home and in the community. Participants will track daily walking volume, walking times on each day, daily knee pain using an NRS (e.g. overall pain, pain during walking), non-walking exercise activities, and any adverse events related to their knees or walking. Additionally, an 11-point numerical rating scale will be used to report weekly confidence in how accurately the FPA modification was performed (0 = “no confidence at all/unable to perform” and 10 = “completely confident”) and difficulty in performing the modification (0 = “not difficulty” and 10 = “most difficult/unable to perform”). A minimum of 10-minutes of daily walking will be requested to ensure enough data for the analysis.

Data processing and analysis

Marker-based motion capture data (as collected during the baseline and follow-up assessments) will be processed using commercially available software and using standard techniques our research group has established [5, 11, 19, 20]. Sensorized shoe data captured during the baseline and follow-up gait assessment, practice sessions, and at-home or community walking will be processed using custom MATLAB scripts. A trained research assistant, blinded to group allocation, will perform all data processing and analysis.

References

- [3] Richards R, van der Esch M, van den Noort JC, Harlaar J. The learning process of gait retraining using real-time feedback in patients with medial knee osteoarthritis. *Gait Posture.* 2018;62:1-6.

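### Adverse-event capture rests on participants' own tracking of knee- or walking-related events, with no stated staff enquiry, withdrawal follow-up or harms summary, so under-counting is likely but of unknown size

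*Protocol*

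**What the plan says.** The Protocol mentions adverse events once, under Gait modification intervention. After describing a booklet on "how to care for and use the sensorized shoes while at home and in the community", it states: "Participants will track daily walking volume, walking times on each day, daily knee pain using an NRS". The same list continues with "non-walking exercise activities, and any adverse events related to their knees or walking". The participant is the recorder, and relatedness to the knees or walking decides what is recorded.

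Staff contact is frequent: "Both groups will attend six practice sessions conducted weekly, which will last approximately 1 hour each". The session leader is described this way: "Practice sessions will be led by a kinesiologist with experience delivering gait modification interventions". No duty to ask about or record adverse events is attached to that role. The symptom measures in sessions are knee pain, where "participants will be asked to rate their knee pain at the beginning, middle, and end of the session", and a difficulty rating at the end.

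The 7-week assessment (Protocol, Baseline and follow-up data collection) lists knee-pain, KOOS and pain-catastrophizing questionnaires, a timed stair climb and gait analysis. The Participants section allows for 15% attrition, but neither document describes a contact at withdrawal. The SAP plans analyses of learning, biomechanical, clinical and difficulty outcomes and none of adverse events.

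**The concern.** The intervention changes foot rotation for six weeks in people aged 50 or over with painful knees, with practice encouraged in daily walking. Sessions include treadmill walking, a dual task and stairs: "transfer testing will be performed during stair ascent and descent in the same manner as the baseline assessment". Effects away from the knee are foreseeable; the Protocol itself cites a study of ankle and rearfoot biomechanics during toe-in and toe-out walking.

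The rule applies a relatedness filter before anything is written down, and the person applying it is the participant. Someone with new hip or back discomfort who does not connect it with walking has no reason to record it. Participants also know whether they were given a 15° target or left to choose a comfortable change, so the filter could work differently in the two arms. That is a risk, not something the documents show.

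What is at stake is how a short adverse-event list would be read. It could reflect good tolerance or the collection rule, and the data would not tell the two apart.

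**Working it through.** **Step 1. Where could an event be picked up?** This compares the sections that describe participant contact.

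| Point of contact | What is stated | What is not stated |
|---|---|---|
| Participant tracking (Gait modification intervention) | Events related to knees or walking; daily knee pain | Events the participant links to neither; when entries are handed in |
| Six sessions (same section) | Knee pain three times; difficulty once | Staff enquiry; staff record of a stumble or a symptom elsewhere |
| 7-week visit (Baseline and follow-up data collection) | Questionnaires, stair climb, gait analysis | An adverse-event question |
| Withdrawal (Participants) | 15% attrition allowance | Any contact, event enquiry or reason for stopping |
| Analysis (SAP) | Learning, biomechanical, clinical and difficulty outcomes | Any harms summary |

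**Step 2. What does the rule admit?** It covers the knees or walking, names no body site and sets no location limit. A foot or hip symptom that the participant attributes to walking is inside it, and so is a stumble on the treadmill. A symptom attributed to neither is outside it. Events inside the rule still depend on the participant writing them down.

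**Step 3. Attrition.** Reproducing the plan's figure: 30 / (1 − 0.15) = 35.3, rounded up to 36 with equal arms of 18. The allowance is 36 × 0.15 = 5.4, so about 5 participants for whom no method of obtaining adverse events is stated.

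**Step 4. Illustration with assumed values.** The documents give no adverse-event rate and no capture proportion. Let *p* be the assumed true risk per participant and *c* the assumed proportion of affected participants with a recorded event, with n = 18 per arm. The expected number with a recorded event is 18*pc*, and the chance that the arm shows none is (1 − *pc*)^18.

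| *p* | *c* | Expected per arm | Chance of none |
|---|---|---|---|
| 10% | 100% | 1.8 | 0.90^18 = 15% |
| 10% | 70% | 1.3 | 0.93^18 = 27% |
| 10% | 50% | 0.9 | 0.95^18 = 40% |
| 20% | 100% | 3.6 | 0.80^18 = 2% |
| 20% | 70% | 2.5 | 0.86^18 = 7% |
| 20% | 50% | 1.8 | 0.90^18 = 15% |

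**Step 5. What the sample could show at best.** With complete capture and 0 events in 18, the one-sided 95% upper bound is 1 − 0.05^(1/18) = 15%.

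**The case against.** A reader might infer that other-site symptoms, events in the laboratory and dropouts' events are all lost, and that harms are under-counted as a matter of fact. The documents do not support that.

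- **Other sites and sessions.** The words about walking admit symptoms at other sites and stumbles during practice. What is missing for sessions is a staff record; the events themselves are not excluded.
- **Dropouts.** The Protocol does not say when tracked entries are collected. Participants attend weekly, so entries made before dropout may well be in hand. Loss is possible but not stated.
- **Related measures.** Knee pain is tracked daily and rated in every session, and NRS pain and KOOS are taken at baseline and follow-up. Worsening knee pain would therefore be visible without the adverse-event item. The two assessments are described as identical and include medical history recorded by the assessor, which might elicit something at 7 weeks, although it is not an adverse-event question.
- **Unseen text.** Consent pages are not part of the supplied text, so any reporting instruction there cannot be checked.
- **Importance.** No hypothesis from H1 to H6 concerns adverse events, and the difficulty and pain outcomes that bear on tolerability do have planned analyses. With 18 per arm, no collection rule would settle safety.

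All of this stands, and it limits the point. It does not remove it. None of these measures asks openly about new symptoms, injuries or falls, and the stated rule still leaves out what the participant does not attribute to knees or walking.

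**Conclusion.** The point holds in limited form. Within the supplied documents, adverse-event capture is confined to self-tracking filtered by relatedness to the knees or walking. No staff ascertainment, withdrawal enquiry or harms summary is stated. Under-counting is likely, because unprompted and filtered self-recording is the only route.

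Its size cannot be derived. The move from 15% to 40%, or from 2% to 15%, in the chance of an event-free arm rests wholly on assumed risks of 10% and 20% and an assumed capture of one half. A difference in under-counting between arms is possible but unsupported by any figure. Nothing here affects the primary outcome or the sample size. It is a worthwhile, inexpensive improvement to safety reporting in a small exploratory trial.

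**What to change.** 1. Reword the tracked item to any new or worsened symptom, injury, stumble or fall, at any body site, whatever its presumed cause.
2. Have staff ask the same open question, in the same words in both arms, at each of the six sessions and at the 7-week visit. Ask it of anyone who withdraws, at the contact when they stop, and record the reason for stopping.
3. Have staff note events they see during treadmill, dual-task and stair tests.
4. Have any relatedness judgement made by someone blinded to arm, such as the blinded research assistant named under Data processing and analysis, or report all events regardless of relatedness. Relatedness assigned by the trainer, who is told the allocation, would leave the attribution problem in place.
5. Add to the SAP a descriptive summary of participants with at least one event by randomised arm, with an exact confidence interval and no test.

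The visits already take place. The added work is one question per visit, a short record at withdrawal, classification of events and one table. The downside is more minor, unrelated events to record and classify, and a reported event rate that looks less favourable.
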